7.3.1 Sample identification

All the IBD services have been identified via the IBD-UK audit, the data of which is publicly available. Identification of IBD nurses will be via the IBD services. Men with IBD will be identified through Crohn's and Colitis UK, poster and leaflet advertising in IBD services and targeted advertising in health and social care organisations that serve under-represented regions and demographic groups. There will be no payment for participation in the survey. However, a prize draw will be offered both for IBD nurses and patient participants offering 1x £50 high-street voucher for the IBD nurse survey and 5 x £50 high-street vouchers for men with IBD. To enter the prize draw a separate part of the survey will collect contact details, which will be stored separately from the survey data and deleted as soon as the prizes winners have been randomly selected and contacted.

Identification of participants for interviews and focus groups will be through the survey and/or study advertisements where participants will be provided the opportunity to express an interest and provide their contact details. Men with IBD and partners of men with IBD will be offered a £20 high-street voucher for participation in the interviews. Professionals will be offered a £20 high-street voucher for participation in the focus groups. All participants will be compensated for travel and other reasonable expenses such as childcare.

Participants for the co-production workshop will be identified by the study team and stakeholder advisory group. Those who participated in interviews and focus groups may also be purposively identified and invited to participate.

Throughout this study, no NHS patient records or data will be used for the identification of participants. NHS sites will be asked to advertise the study using posters, leaflets and social media but no patient details will be passed from NHS sites to the study team.

7.3.2 Consent

WS1: Surveys

FUNDED BY

National Institute for
Health and Care Research

York and Scarborough
Teaching Hospitals
NHS Foundation Trust

Est. 1841 YORK ST JOHN UNIVERSITY

MenSH-IBD

The online survey data is anonymous at point of entry and therefore written informed consent will not be taken. However, the survey will have an opening information page explaining the study and how the data will be used. Participants will be asked to select a box to confirm they have read and understand this information. At the end of the survey there will be two further optional additions (1) to enter a prize draw: participants will be asked to select a box to consent to their contact details to be held separately from the survey responses, only for the purpose of awarding the prize and until completion of the survey, after which all data will be deleted, (2) to express an interest in participating in an interview: participants will be asked to select a box to consent for their contact details alongside the demographic details page to be sent to the study team and stored until the end of the study for the purpose of contact the participant about this study only.

WS2 and WS3: Interviews, focus groups and co-production workshops

Written informed consent will be obtained prior to participation in interviews, focus groups or co-production workshops. The process of obtaining informed consent will be in accordance with Good Clinical Practice (GCP). Participants will be provided with a participant information sheet and given time to consider the information and the opportunity to ask the study team questions. As most of this work will be conducted remotely, on-line consent will be available in this study.

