Data will be analysed descriptively using appropriate summary statistics (frequencies/percentages for categorical variables; means/standard deviations or medians/quartile ranges for continuous variables, depending on their distribution). For key variables and scores, 95% confidence intervals will be presented and differences between geographical regions evaluated. Differences between centres that responded and those that did not will be tested using available information. Several associations including barriers and facilitators with the offer of a sexual health assessment for men will be tested using logistic regression. A similar approach will be applied to other key variables and scores as identified by the advisory group and across the three surveys. In each case, estimates of the magnitude of association, for example odds ratio, and corresponding 95% confidence intervals will be presented. Where it is feasible to do so differences between geographical regions and demographic characteristics, such as ethnicity and under-researched populations will be presented. We will assess the mechanism of missing values: if there is a need to impute missing values we will use multiple imputations as a sensitivity analysis.

WS2. Qualitative study

Concurrent with WS1 a qualitative study will be carried out. This will involve: (i) in-depth individual semi-structured interviews with men with IBD and their partners; and (ii) focus groups with nurses and other clinicians involved in the provision of care to men with IBD. The aim of this stream is to explore factors identified in our preliminary PPI work that influence the sexual health assessment and care of men with IBD, and generate ideas on appropriate and acceptable ways in which this could be improved as a basis for the design of the intervention in WS3.

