7.2.2 Sampling technique

WS1. Cross-Sectional Surveys

(WS1.1) Census approach of all IBD services as identified by the 2019 IBD-UK audit.

(WS1.2) Census approach of all IBD specialist nurses.

(WS1.3) Targeted convenience sampling of men with IBD via established networks.

WS2 and WS3 Qualitative study and co-production workshops

Purposive sampling will be adopted in workstreams 2 and 3. For the interviews a heterogenous sample who indicate a willingness to be interviewed in the patient survey in WS1 will be purposively recruited based on a range of characteristics including age, ethnicity, marital/partner status, sexuality, and IBD type (UC or Crohn's). Participants with partners will be asked to invite them to participate should they wish. For the focus groups a multidisciplinary sample of participants (e.g., nurses, doctors, allied health professionals, psychologists) involved in the provision of IBD care in the NHS setting will be purposively recruited.

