8 ETHICAL AND REGULATORY CONSIDERATIONS

8.1 Assessment and management of risk

Risk to participants: This is a low-risk study as no clinical intervention is being performed. There is no expected risk to participants, but for those participating in the surveys or interviews there is potential for an emotive response to be elicited. The final page of the public-facing survey will signpost people to relevant organisations that can provide additional support. For the interviews and focus groups, the researcher will be either a registered nurse or experienced qualitative researcher and can respond to any emotional distress and escalate accordingly. Interviews will be terminated if it is felt that they are negatively impacting on a participant. Participants will be offered the Participant Support Leaflet which will provide a list of helpful resources and signpost access to support for depression, anxiety and stress. If any safeguarding issues are disclosed during the interviews they will be escalated via the appropriate channels. There may be some inconvenience to participants regarding the time taken to participate. Participants will be offered a range of possible dates and times.

FUNDED BY

National Institute for
Health and Care Research

York and Scarborough
Teaching Hospitals
NHS Foundation Trust

Est. 1841 YORK ST JOHN UNIVERSITY

MenSH-IBD

Risk to researchers: The study setting carries very little risk to the researchers. Researchers interviewing or facilitating focus groups will be supported by SM or PG who are experienced nurses and researchers. Research debriefs will be offered with either SM or PG.

Informed consent: The process for obtaining informed consent will be in accordance with Good Clinical Practice. In WS1 no identifiable information is collected and therefore there will be no associated consent form. Surveys will instead have an opening page explaining the details of the study and how data collected will be stored and used. The participant will have to select a tick box to say they have understood the information and then completion of the survey will indicate consent. At the end of the surveys, participants may opt-in to a prize draw for participation by providing their email and providing consent for this to be stored until the prizes are allocated. This list will be kept separately to the research data and deleted as soon as the prizes have been randomly allocated.

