In WS2 and WS3, potential participants will be given suitable time to consider the written information provided to them and discuss any queries with the research team or others. Participants will be given the opportunity to ask any questions and have any queries answered. The study consent form must be signed and dated by the participant before participation in the interview, focus group or workshop and the collection of any data. This study will offer electronic consent which is proportionate to these non-interventional studies low risk of harm to participants.

Enrolment log: there will be an enrolment log for WS2 and WS3. This (alongside the consent forms) will be the only location of written personal information that is not anonymised. It is necessary for the purpose of contacting participants and quality assurance of the research. It will be password protected and kept on the secure digital network of the Sponsor separately to the research data. It will only be accessible to those signed on the delegation log.

Audio recordings: these are required for audio-transcription of the interviews and focus groups. These must be immediately downloaded onto the secure network drive of either York and Scarborough Teaching Hospitals NHS Foundation Trusts or the University of York (both of whom have security arrangements and standard operating procedures for the storage of data in research trials at the end of the interview and deleted from the original recording device or one-drive if video conferencing. Audio recordings may be identifiable so for additional security these files should be password protected and deleted at the end of the study. Audio recordings will be deleted once data analysis is complete.

FUNDED BY

National Institute for
Health and Care Research

York and Scarborough
Teaching Hospitals
NHS Foundation Trust

Est. 1841 YORK ST JOHN UNIVERSITY

MenSH-IBD

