8.6 Data protection and patient confidentiality

Data management will comply with the Data Protection Act (2018), GDPR regulations (2016) and York and Scarborough Teaching Hospitals NHS Foundation Trust research SOPs. All investigators and study staff will comply with the Data Protection Act in regards to the collection, storage process and disclosure of personal information.

FUNDED BY

National Institute for
Health and Care Research

York and Scarborough
Teaching Hospitals
NHS Foundation Trust

Est. 1841 YORK ST JOHN UNIVERSITY

MenSH-IBD

All data will be stored and archived by York and Scarborough Teaching Hospitals NHS Foundation Trust in line with their current research SOPs. In WS1 no identifiable information will be collected as part of the research. Participants can opt-in to a prize draw for completion of the survey at which point they will be asked to select a tick-box allowing their email address to be kept until the prizes have been randomly awarded. This list will be kept separately from the study data and deleted once the prizes have been awarded.

In WS2 and WS3 study number and pseudonym will be assigned to each participant. The study number will be allocated by the research team and used on the study documents including the CRF and transcripts. A pseudonym will be used within the interviews and transcriptions and will be selected randomly from a pre-defined list. A separate document will provide a list of study numbers and participant names. As this document will contain identifiable information it will only be accessible by appropriate study members signed on the site delegation log for the purposes of conducting the research and auditing. This will include the CI and York Teaching Hospital Quality Assurance Lead. The document will be stored separately from the site file and trial data and be password protected.

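### Does the WS1 interview-interest list, which joins contact details to the demographic page, undermine the statements that WS1 collects nothing identifiable?

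*Protocol*

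**What the plan says.** Section 7.3.2 (WS1) starts from anonymity: "The online survey data is anonymous at point of entry and therefore written informed consent will not be taken". It then describes two optional additions at the end of the survey. Prize-draw contact details are kept apart from the answers and deleted afterwards. For interview interest, a separate tick box covers "contact details alongside the demographic details page to be sent to the study team and stored until the end of the study", to be used only for contact about this study. Section 7.3.1 confirms the route: "participants will be provided the opportunity to express an interest and provide their contact details". Section 7.2.2 explains why demographics go with the contact details: interviewees are chosen purposively, "based on a range of characteristics including age, ethnicity, marital/partner status, sexuality, and IBD type".

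Three later statements do not mention this list:

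- Section 8.1, informed consent: "In WS1 no identifiable information is collected and therefore there will be no associated consent form".
- Section 8.1, enrolment log for WS2 and WS3: "This (alongside the consent forms) will be the only location of written personal information that is not anonymised".
- Section 8.6: "In WS1 no identifiable information will be collected as part of the research".

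The consent paragraph of section 8.1 and the WS1 text of section 8.6 both go on to describe an opt-in, but only the prize draw.

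**The concern.** A list of contact details joined to demographics is identifiable, it is gathered through the WS1 surveys, and it is neither the enrolment log nor a consent form. Read word for word, all three later statements are untrue for the men on it. Two of the anonymity statements, in sections 7.3.2 and 8.1, are also the stated reason for having no WS1 consent form.

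There is a practical side as well. The survey file must hold similar characteristics, since section 5 (analysis of quantitative data) says that, where feasible, "differences between geographical regions and demographic characteristics, such as ethnicity and under-researched populations will be presented", and section 7.2.1 foresees results by age group, sexuality and ethnicity. Under section 8.8 the core team sees the full dataset. If a man on the list has a combination of characteristics that no other respondent shares, his answers on sexual health care could be matched to his name. Men with rarer profiles, whom the study particularly wants to reach, are the most exposed. At stake are confidentiality and the accuracy of what respondents are told.

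**Working it through.** **Text comparison.** No protocol figure depends on this point, so there is none to reproduce.

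| Question | Prize-draw list | Interview-interest list |
|---|---|---|
| Collected through WS1? | Yes | Yes |
| Own opt-in box? | Yes (7.3.2) | Yes (7.3.2) |
| Stated purpose and end date? | Award of prizes, then deletion | Contact about this study, to end of study |
| Held apart from survey answers? | Stated | Not stated; travels with the demographic page only |
| Mentioned in 8.1 and 8.6? | Yes | No |
| Covered by the general rules in 8.6 (data protection law, delegation-log access, two secure networks)? | Yes | Yes |

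Two things follow. First, sections 8.1 and 8.6 call WS1 non-identifiable and at once describe an opt-in email list, so their authors are speaking of the survey data and treating opt-in contact details as something beside them. Section 8.6 says as much by limiting its statement to what is collected as part of the research. Secondly, the claim about a sole location stands in a paragraph on WS2 and WS3. It cannot be meant for the whole study, because it would also exclude the prize-draw list described in the preceding paragraph. This is an incomplete enumeration.

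**How many men might be linkable?** The protocol gives neither the demographic categories nor the share who will opt in, so what follows is assumption. Simulation: 2,000 samples of 378 men, the five characteristics of section 7.2.2 drawn independently, counting men whose combination occurs once. Assumed shares in per cent, coarse then usual categories:

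- ethnicity 90/10 or 90/5/2/2/1
- sexuality 88/12 or 88/8/3/1
- partner status 70/30 or 65/25/10
- IBD type 50/50 or 47/47/6
- age 20/30/30/20 or 8/18/20/20/18/16
- region, where added, 12 equal groups

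The list is assumed to hold 10-30% of respondents: 378 × 0.10 = 38 to 378 × 0.30 = 113. Men on the list are taken to resemble all respondents.

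| Assumed categories | Cells | Unique among 378 | Unique men on the list |
|---|---|---|---|
| Coarse | 2×2×4×2×2 = 64 | 2.9% | 38 × 0.029 = 1 to 113 × 0.029 = 3 |
| Usual survey categories | 5×4×6×3×3 = 1,080 | 14.9% | 38 × 0.149 = 6 to 113 × 0.149 = 17 |
| Usual plus 12 regions | 1,080 × 12 = 12,960 | 54.1% | 38 × 0.541 = 21 to 113 × 0.541 = 61 |

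Applied to all 378 respondents, the same percentages give 11, 56 and 204 men. Those counts do not measure exposure, because a man who leaves no contact details cannot be matched to a name; 204 is larger than the longest list assumed. Region is not among the characteristics named in section 7.2.2. Among men who are non-heterosexual or of minority ethnicity, the unique shares are about 14%, 62% and 95%, so the direction of the concern is right. The shares fall if more men answer, which section 7.2.1 allows for: with 1,000 respondents they are 0.7%, 8.3% and 33%.

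**The case for a change.** The strongest case for a change is this. Anonymity is given as the reason for taking no consent form, so an inaccurate statement supports the consent model. The qualifier in section 8.6 does not rescue the unqualified sentence in section 8.1, and choosing interviewees is itself part of the research. An enrolment log does not obviously cover people who are never enrolled. The tick box covers being contacted; it is not described as covering possible linkage of answers already given as anonymous.

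Part of this stands. The sentences are incomplete as written, and linkage is possible in principle for a man on the list with a unique profile.

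The rest carries less weight. The identifiable part has its own consent step, so nobody's contact details are taken without agreement. Only the demographic page goes with them, not the answers on sexual health. Matching would take a deliberate act by staff bound by the delegation log and data protection law. The information sheet and the survey itself are listed in Appendix 1 but not reproduced, so what respondents are told about linkage is unknown.

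The obvious remedies gain little. A separate short form with the same five characteristics in broad bands could still be matched: that is the coarse row above. Broader bands would also cost detail in a purposive selection that seeks variety. Early deletion of those not invited, 38 − 20 = 18 to 113 − 15 = 98 men under the same assumptions if 15-20 are interviewed, overlooks two points. Interview numbers depend on saturation, so a reserve is useful, and section 7.3 uses the same expressions of interest for WS3, which runs in the last months of the study.

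**Conclusion.** The inconsistency is real but clerical. Sections 8.1 and 8.6 leave out a list that section 7.3.2 describes openly, with consent, purpose and retention stated, and that the general rules of section 8.6 already govern. A study team following the protocol would handle the list under those rules.

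Keeping demographics with contact details is a fair trade-off, because purposive sampling cannot be done without them. The residual linkage risk is confined to men who opt in and have a unique profile. Its size cannot be derived from the protocol: the span of about 1 to 61 men rests on assumed categories, population shares, independence and opt-in rate. The survey targets, margins of error, planned estimates and conclusions are the same whichever way the sentences are worded. No change to the plan follows.

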8 ETHICAL AND REGULATORY CONSIDERATIONS

8.1 Assessment and management of risk

Risk to participants: This is a low-risk study as no clinical intervention is being performed. There is no expected risk to participants, but for those participating in the surveys or interviews there is potential for an emotive response to be elicited. The final page of the public-facing survey will signpost people to relevant organisations that can provide additional support. For the interviews and focus groups, the researcher will be either a registered nurse or experienced qualitative researcher and can respond to any emotional distress and escalate accordingly. Interviews will be terminated if it is felt that they are negatively impacting on a participant. Participants will be offered the Participant Support Leaflet which will provide a list of helpful resources and signpost access to support for depression, anxiety and stress. If any safeguarding issues are disclosed during the interviews they will be escalated via the appropriate channels. There may be some inconvenience to participants regarding the time taken to participate. Participants will be offered a range of possible dates and times.

FUNDED BY

National Institute for
Health and Care Research

York and Scarborough
Teaching Hospitals
NHS Foundation Trust

Est. 1841 YORK ST JOHN UNIVERSITY

MenSH-IBD

Risk to researchers: The study setting carries very little risk to the researchers. Researchers interviewing or facilitating focus groups will be supported by SM or PG who are experienced nurses and researchers. Research debriefs will be offered with either SM or PG.

Informed consent: The process for obtaining informed consent will be in accordance with Good Clinical Practice. In WS1 no identifiable information is collected and therefore there will be no associated consent form. Surveys will instead have an opening page explaining the details of the study and how data collected will be stored and used. The participant will have to select a tick box to say they have understood the information and then completion of the survey will indicate consent. At the end of the surveys, participants may opt-in to a prize draw for participation by providing their email and providing consent for this to be stored until the prizes are allocated. This list will be kept separately to the research data and deleted as soon as the prizes have been randomly allocated.

In WS2 and WS3, potential participants will be given suitable time to consider the written information provided to them and discuss any queries with the research team or others. Participants will be given the opportunity to ask any questions and have any queries answered. The study consent form must be signed and dated by the participant before participation in the interview, focus group or workshop and the collection of any data. This study will offer electronic consent which is proportionate to these non-interventional studies low risk of harm to participants.

Enrolment log: there will be an enrolment log for WS2 and WS3. This (alongside the consent forms) will be the only location of written personal information that is not anonymised. It is necessary for the purpose of contacting participants and quality assurance of the research. It will be password protected and kept on the secure digital network of the Sponsor separately to the research data. It will only be accessible to those signed on the delegation log.

Audio recordings: these are required for audio-transcription of the interviews and focus groups. These must be immediately downloaded onto the secure network drive of either York and Scarborough Teaching Hospitals NHS Foundation Trusts or the University of York (both of whom have security arrangements and standard operating procedures for the storage of data in research trials at the end of the interview and deleted from the original recording device or one-drive if video conferencing. Audio recordings may be identifiable so for additional security these files should be password protected and deleted at the end of the study. Audio recordings will be deleted once data analysis is complete.

FUNDED BY

National Institute for
Health and Care Research

York and Scarborough
Teaching Hospitals
NHS Foundation Trust

Est. 1841 YORK ST JOHN UNIVERSITY

MenSH-IBD

Recruitment: No coercion or undue influence to take part will be used. Participants will be made aware that participation is voluntary, and they are free to withdraw at any point without giving a reason. Any participants who are experts through experience of living with IBD will be informed that participation in the study will not alter their clinical care. Participants that are experts through experience who are involved in interviews or co-production will be offered a £20 high-street voucher for participation. Professionals who are involved in focus groups will be offered a £20 high-street voucher. There will be a £50 prize draw for participation in the on-line surveys.

Deception: No misleading information will be given and no intentional deception used.

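### The only support measure the protocol describes for the men's survey is on its last page, so a respondent who stops early would not see it

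*Protocol*

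**What the plan says.** Section 8.1 rates the study as low risk but names one hazard, and applies it to surveys as well as interviews: "for those participating in the surveys or interviews there is potential for an emotive response to be elicited". The sentence that follows gives the measure for the survey: "The final page of the public-facing survey will signpost people to relevant organisations that can provide additional support". The public-facing survey can only be WS1.3, because Section 5 sends WS1.1 to service leads and WS1.2 to nurses.

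The opening page is described in two places. Section 7.3.2 says "the survey will have an opening information page explaining the study and how the data will be used". The informed-consent paragraph of Section 8.1 says "Surveys will instead have an opening page explaining the details of the study and how data collected will be stored and used".

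Two further statements matter. The recruitment paragraph of Section 8.1 says of participants that "they are free to withdraw at any point without giving a reason". Section 7.3.2 says "The online survey data is anonymous at point of entry", and places the optional collection of contact details at the end of the questionnaire.

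For interviews and focus groups, Section 8.1 provides a registered nurse or experienced qualitative researcher who can respond to distress. It also provides for ending an interview that is harming the participant, and for escalating safeguarding concerns raised in interviews. Among these sentences it adds: "Participants will be offered the Participant Support Leaflet which will provide a list of helpful resources".

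**The concern.** The safeguard depends on completing the survey, while the hazard it addresses is itself a reason not to complete. A respondent upset by the questions may simply close the browser. As the protocol is written, he then leaves without the support information intended for that situation.

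The survey is also the largest patient-facing component, with a target of 378 men against 15 to 20 interview participants (Section 7.2.1). It is completed online, and no researcher is described as present. What is at stake is participant welfare and whether a stated risk control reaches the people it is for. No estimate, margin of error or test depends on it.

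**Working it through.** There is no figure to reproduce, because the protocol attaches no number to this point. The check is to set the relevant statements side by side and follow a respondent who stops part-way through WS1.3.

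1. **Is the hazard acknowledged for the survey?** Yes. Section 8.1 names surveys alongside interviews.
2. **What support is tied to the survey?** One measure, signposting on the final page (Section 8.1).
3. **Does the opening page carry support information?** Not as described. Section 7.3.2 gives its content as the study and the use of data. Section 8.1 gives it as study details and the storage and use of data.
4. **Is there a per-page link or an early-exit page?** None is described in Sections 5, 7.3, 7.3.1, 7.3.2, 8.1 or 8.6.
5. **Can the respondent stop early?** Yes, at any point and without a reason (Section 8.1, recruitment paragraph).
6. **Can the team reach him afterwards?** No. Entry is anonymous, and the optional fields for contact details also come at the end (Section 7.3.2).
7. **Do the other safeguards in Section 8.1 apply?** The researcher's response and the ending of an interview need a live session. Safeguarding escalation is tied to disclosures in interviews. The leaflet sentence follows these and gives no route to an anonymous online respondent.

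Steps 2 to 4 show that the only described support sits at the end of the survey. Steps 5 and 6 show that a man who stops early neither reaches it nor can be contacted. Step 7 shows that nothing else in the section clearly fills the gap.

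The contrast with the interviews is within the protocol itself: stopping early is provided for there and is not provided for in the survey.

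**The case against.** The strongest objection is that the protocol never says signposting appears on the final page alone. The survey (11.1.5) and the information sheet (11.1.1) are listed in Appendix 1 but not shown, and the page layout is settled there. The two descriptions of the opening page are written to explain consent and data handling and need not be complete lists. This stands as a limit: the finding concerns what the protocol describes, not what the instrument contains.

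The leaflet is offered to participants without restriction, so it might be meant for survey respondents too. Its position among the interview and focus-group sentences, and the absence of any delivery route, make that reading weak. If it is intended, Section 8.1 should say how the leaflet reaches them.

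Section 7.3 makes a team member available during working hours to answer questions. Anonymity does not stop a respondent from making contact himself. The route is real, but it is given under recruitment, is not described as distress support and is limited to office hours.

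It can also be said that this is a layout preference. The survey takes no more than 15 minutes, the advisory group with its public members advises on developing and piloting the instruments (Section 8.4), and the study undergoes NHS ethics review (Section 8.2). This supports rating the point as minor. It does not remove it, because the protocol itself judged the survey risk worth a control.

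**Conclusion.** The point holds as a minor one. On the protocol's own description, a man who leaves WS1.3 before the last page, for whatever reason, does not see the support information and cannot be followed up. This assumes that the unseen survey and information sheet add no earlier signposting. If they do, Section 8.1 only needs to say so.

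Three stronger readings are tempting and are not supported.

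- **That nobody who breaks off receives any support information.** This would need the survey and information sheet, which are not shown.
- **That a count of affected men can be given.** If 10% to 30% of starters were assumed to stop and 378 to complete, there would be 378/0.9 = 420 to 378/0.7 = 540 starters, and so 42 to 162 early leavers. The protocol gives no break-off rate, and these figures count everyone who stops, including those short of time or interest. They do not measure distress and should not be used as the size of the problem.
- **That the survey asks about sexual function, incontinence or relationships.** Section 5 lists its domains as including experience of sexual health assessment and intervention, and perceived needs, preferences and barriers. Such questions may occur, but the protocol does not state them, and the point does not need them.

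Sample size, precision and analysis are unaffected.

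**What to change.** First check the survey and the information sheet. If support details already appear before the final page, add a sentence to Section 8.1 saying where.

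If not, amend Section 8.1 so that the signposting planned for the final page also appears on the opening information page and through a persistent link on every page, or on an early-exit page. Keep it on the final page as well. State in the same sentence whether the Participant Support Leaflet is meant for survey respondents and, if so, how they reach it. It should not be assumed to be ready: Section 8.1 describes it in the future tense and Appendix 1 does not list it.

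The cost is a small edit to the survey template and the protocol. It should be logged as a minor amendment; Appendix 3 shows that minor survey changes have already been handled as an amendment. No extra data are collected, no contact with respondents is needed, and anonymity is preserved.
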